1.1. Objectives and Endpoints

| Objective | | | | | |
|---|---|---|--|--|--|
| Clinical | Statistical | | | | |
| Category | Category | Estimand/Variable | | | |
| Primary Objecti | ve: to evaluate th | ne safety and effectiveness of VOLUMA with Lidocaine injectable gel for the | | | |
| improvement of v | olume and aesthe | etic appearance of the nose in a Chinese population. | | | |
| Effectiveness ¹ | Variable: change from baseline in the nose volume calculated by | | | | |
| | | digital analysis of each participant's 3D images at Week 24 | | | |
| | | Population: mITT | | | |
| | | • IES: | | | |
| | | Missing at random will be assumed in an MMRM model, | | | |
| | | therefore no imputation will be conducted | | | |
| PLS: change from baseline between treatment and MMRM | | • PLS: change from baseline between treatment and control groups | | | |
| | | o MMRM | | | |
| | Secondary | Variable: GAIS responder by EI and participant, NSS responder by | | | |
| | | participant at Week 24 | | | |
| | | Population: mITT | | | |
| | | • IES: | | | |
| | | Participants with missing data at Week 24 will not be imputed | | | |
| | | PLS: responder rates between treatment and control groups | | | |
| | | o Fisher's exact test | | | |
| Safety | Primary | Variable: | | | |
| | | o TEAEs | | | |
| | | o ISRs | | | |
| | | Population: Safety Population | | | |
| | | Analysis: Categorical descriptive | | | |

IES = Intercurrent event(s) strategy; PLS = Population-level summary.

¹ All estimand attributes explicitly identified for primary/secondary and select key estimands only.

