5.1. General Considerations

- The primary analysis will be performed after the database is locked and randomization schedule is released.
- Participants will receive treatment at the outset of the study (treatment group) or have treatment delayed until Week 24 (control group). The delayed treatment for control group is optional and referred to as "Optional Treatment".
- Control Period (CP), Treated Period (TP) are defined in Table 5-1.

Table 5-1 **CP and TP definition**

| Randomization | Period | Treatment | Start Date | End Date |
|---------------|--------|------------------------|---------------------------------|---|
| Group | | Group Label | | |
| Treatment | СР | VOLUMA | Initial treatment date | The date of effective assessment for Week 24. If multiple assessments fall into Week 24 window, the date of the assessment included in the Week 24 analysis will be used as end date. For participants who exit before Week 24, the end date is study exit date. For participants with intermittent missing assessment at Week 24, the target day for Week 24 (Day 169) will be the end day. |
| | TP | VOLUMA | Initial treatment date | Study exit date |
| Control | СР | Control | Randomization date | For participants who do not receive optional treatment If multiple assessments fall into Week 24 window, the date of the assessment included in the Week 24 analysis will be used as end date. For participants who exit before Week 24, the end date is study exit date. For participants with intermittent missing assessment at Week 24, the target day for Week 24 (Day 169) will be the end day. For participants who receive optional treatment: The day before optional treatment |
| | ТР | VOLUMA Post-Control | Optional initial treatment date | Study exit date |

JUVÉDERM® VOLUMA® with Lidocaine

- For CP, effectiveness analyses and baseline characteristics will be performed on the mITT population using the "as-randomized" assignment. One of the sensitivity analyses for the primary endpoint will be based on PP population. Safety analyses for CP will be conducted using the Safety Population based on "as-treated" assignment.
- For TP, effectiveness and safety summaries will be performed on the VITP and VOTP using "as-treated" assignment.
- For applicable effectiveness endpoints, baseline is defined as the last non-missing value prior to the start of study treatment for treatment group or no later than randomization date for control group.

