5.6.3. Adverse Events

An AE will be considered a TEAE if the AE began or worsened (increased in severity or became serious) on or after the date (and time, if known) of the initial treatment for treatment group and after randomization for control group.

An AE will be considered a TESAE if it is a TEAE that additionally meets any SAE criterion.

TEAEs will be summarized by treatment group for CP using the Safety population.

TEAEs will also be summarized for TP using VITP and VOTP, respectively.

The number and percentage of participants with TEAEs as well as the events in the following AE categories will be summarized for the above populations as described in Table 5-7.

If more than 1 AE is coded to the same preferred term for the same participant, the participant will be counted only once for that preferred term using the most severe and most related occurrence for the summarizations by severity and by relationship to study intervention.

Listings of all TEAEs, TESAEs, TEAEs leading to discontinuation, and death will be presented.

Table 5-7 TEAE Summaries

| Endpoint | Description | Timing | Methodology |
|--------------------------------|--|--------|--|
| Overall summary | Overall summary only for the following categories: TEAEs Treatment-related TEAEs Treatment-related TEAEs at injection site Treatment-related TEAEs not at injection site TESAEs Treatment-related TESAEs Treatment-related TESAEs Treatment-related TESAEs at injection site Treatment-related TESAEs not at injection site Discontinued due to TEAE Deaths | CP, TP | Categorical descriptives, event descriptives |
| TEAEs | Overall summary and by SOC and PT Overall summary and by SOC, PT, and maximum severity | CP, TP | Categorical descriptives, event descriptives |
| Treatment-related TEAEs | Overall summary and by SOC and PT Overall summary and by SOC, PT, and maximum severity Overall summary by maximum severity, time to onset, duration, action taken and outcome | CP, TP | Categorical descriptives, event descriptives |
| TESAEs | Overall summary and by SOC and PT | CP, TP | Categorical descriptives, event descriptives |
| AEs leading to discontinuation | Overall summary and by SOC and PT | CP, TP | Categorical descriptives, event descriptives |

SAP 1894-701-008 amendment 1

5.6.4. **Injection Site Response**

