6.4.2.1. Missing/Incomplete AE Start Date

For scenario 2, i.e. if day is missing but month and year are available, then the imputed day will be the first day of the month or the initial injection date (randomization date for control group) if they have the same month and year, whichever is later (because TEAE onset is not expected prior to administration of study treatment);

For scenario 4, i.e. if day and month are missing but year is available, then the imputed day and month will be 01 Jan or the initial injection date (randomization date for control group) if they have the same year, whichever is later;

For scenario 8, i.e. if day, month and year are all missing, impute start date as the earliest possible date on or after initial injection date for treatment group. And impute start date as the earliest possible date on or after randomization date for control group.

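### SAP 6.4.2.1 anchors incomplete adverse event start dates for all controls at randomization, so some events after the optional injection would be dated into the untreated period; SAP 5.1 also leaves the baseline after that injection unclear

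*SAP*

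**What the plan says.** **AE start dates.** SAP 6.4.2.1 covers three kinds of incomplete date.

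- Day missing: "the imputed day will be the first day of the month or the initial injection date (randomization date for control group"), whichever is later, if month and year agree.
- Day and month missing: "the imputed day and month will be 01 Jan or the initial injection date (randomization date for control group"), whichever is later, if the year agrees.
- Everything missing: "And impute start date as the earliest possible date on or after randomization date for control group".

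In each case randomization replaces the injection date for controls. Nothing is said about controls who later take the optional injection.

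**Periods and tables.** For optionally treated controls, SAP Table 5-1 ends the Control Period (CP) on "The day before optional treatment" and starts the Treated Period (TP) on the optional initial treatment date. SAP 5.6.3 states: "TEAEs will be summarized by treatment group for CP using the Safety population". It summarizes TP events separately for the VOLUMA Optionally Treated Population (VOTP). Its onset rule for a treatment-emergent AE (TEAE) in controls refers to randomization only. For treatment-related TEAEs, Table 5-7 adds, for both periods, "Overall summary by maximum severity, time to onset, duration, action taken and outcome". SAP 1.1 names TEAEs as a primary safety variable, with "Analysis: Categorical descriptive".

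**Volume baseline.** SAP 5.1 defines the effectiveness baseline as the last value before study treatment for the treatment group, or "no later than randomization date for control group". The protocol synopsis (Post-control Period, control group) makes the Week 24 pre-injection image the baseline for volume change after optional treatment. SAP 5.3.4 summarizes VOTP volume change without naming a baseline, and Appendix 2 (SAP 6.2) lists no baseline change.

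**The concern.** The imputed start date decides which period, and so which column, an event enters. An AE that follows the optional injection but carries an incomplete date can be imputed to a day before the injection. It then leaves the VOTP table and enters the no-treatment column of the randomized safety comparison. That direction is not conservative for device safety. If the investigator judged the event related to treatment, a treatment-related AE appears under Control, with onset and duration counted from a day before any device exposure. SAP 6.4.2.1 gives as its reason for the anchor that onset is not expected before study treatment; for these participants the rule produces just that.

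The baseline question concerns only the descriptive VOTP volume summary. If the control clause of SAP 5.1 were programmed for VOTP, the post-injection change would include the 24 untreated weeks.

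**Working it through.** **The plan's own figure.** No stated figure depends on this point. The 99.6% power for 90 versus 30 participants (difference 0.9 mL, SD 0.9 mL) reproduces: noncentrality 0.9 / (0.9 × √(1/90 + 1/30)) = 4.74, df 118, power 99.7%. Nothing below changes it.

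**Example (illustrative dates).** Randomized 5 March 2018, injected 26 August 2018 (174 days later), AE on 28 August 2018. Recorded as August 2018, it is imputed to 1 August. Recorded as 2018 only, or left blank, it is imputed to 5 March. All three fall in the untreated period.

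**Inputs.** Optional injection at most 10 days after the Week 24 visit (protocol 6.2.3.2), so 168 to 178 days after randomization. Assumptions: injection dates spread evenly over four calendar years (1,461 days, 48 months); true onset uniform over *k* days from injection.

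**Month-only dates** are misplaced when onset falls in the injection month, unless the injection was on the 1st. For a month of *L* days, the at-risk days summed over injection days are L(L−1)/2. Over four years: 28×465 + 16×435 + 3×378 + 1×406 = 21,520. Mean 21,520/1,461 = 14.73 days, and the share is 14.73/k.

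**Year-only dates** are misplaced when onset falls in the injection year, unless the injection was on 1 January. For a 365-day year the share is [k(k+1)/2 + (364−k)k] / (365k). At k = 168: (14,196 + 32,928)/61,320 = 76.9%.

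| Onset within | Month-only | Year-only |
|---|---|---|
| 56 days | 26.3% | 92.2% |
| 168 days (24 weeks) | 8.8% | 76.9% |
| 224 days (with touch-up) | 6.6% | 69.2% |

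**Wholly missing dates** go to randomization, and so are always misplaced, if nothing else bounds the earliest possible date.

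**How far.** With onset over 168 days, misplaced events are dated 1–30 days before injection (month-only, mean 10.5), 1–178 days (year-only, mean 118–122) or 168–178 days (wholly missing).

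**Weight of one participant.** 1/40 = 2.5 points in the Control column, against 1/120 = 0.8 points in the VOLUMA column.

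**What a remedy can misplace.** Take true CP onset uniform over 178 days, with injection 10 days after Week 24.

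- Re-anchoring every compatible date at the injection, with no other information, moves 100% (wholly missing), 76% (year-only) and 8% (month-only) of true CP events into TP.
- If first-report information exists and AEs are reported at the next visit, only the last 10 days are at risk: 10/178 = 5.6% (wholly missing); 9.85/178 = 5.5% (year-only); 8.19/178 = 4.6% (month-only). With injection on the day of the Week 24 visit it is zero.

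The break-even share of such events that must truly be post-injection is remedy error / (remedy error + current error). In the same order:

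- No information: 1/(1+1) = 50%; 0.755/(0.755+0.769) = 50%; 0.083/(0.083+0.088) = 49%.
- Full first-report information: 0.056/1.056 = 5%; 0.055/0.824 = 7%; 0.046/0.134 = 34%.

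**Baseline.** On the planning value for controls (SAP 3) the shift is 0.2 mL, or 0.2/1.1 = 18% of the assumed treated change. For an assumed control change of 0 to 0.3 mL it is 0 to 27%. It is zero if the protocol rule is programmed.

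**The case against.** **The effect may be nil.** AEs are queried at each post-baseline visit (protocol 11.1.1), recorded on awareness (11.2) and source-verified (7.5), and eCRF queries are issued (12.4.2). Few dates may be incomplete. Diary injection site responses and fully dated AEs fall outside the rule, and the CP comparison is descriptive, without a test. All of this stands and limits the size. It does not supply the missing exception. SAP 5.6.3 lists all TEAEs, so a misplaced event could be noticed, but no rule corrects it.

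**All wholly missing dates misplaced?** A reader might infer this as a certainty. The SAP does not define the earliest possible date. If a programmer bounds it by other data, some events would be placed correctly.

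**Always 2.5 points?** Tables count participants, so the addition occurs only if that participant has no other CP event in the same row.

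**Does the SAP contradict the protocol on baseline?** A reader might infer an undeclared departure. The visible text does not establish one. The bullet just before the baseline definition in SAP 5.1 analyzes TP as treated. Read with it, a treated control can fall under the clause for values before the start of study treatment, which is the image the protocol names. The SAP Version History ties the control clause to baseline photographs taken after randomization because of an imaging set-up error, not to the post-control baseline. Protocol 8.2.1 and SAP 5.1 agree for the primary comparison. Parts of the SAP are not visible and the table shells are a separate document. An ambiguity remains, no more.

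**Anchor everything at the injection instead?** Without other information this exchanges one error for another, with break-even near 50%. The objection stands, so the remedy must depend on evidence about each event.

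**Conclusion.** The AE date rule is wrong as written for optionally treated controls. A post-injection AE with a month-only date in the injection month, a year-only date in the injection year, or a wholly missing date (if nothing else bounds it) is generally dated before the injection and counted under Control in CP rather than under VOTP in TP. Injection on the 1st of the month, or on 1 January, is the exception for the first two kinds.

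Under uniform onset over 24 weeks, about 9% of month-only and 77% of year-only dates are misplaced. These are shares of incomplete post-injection dates, not of all AEs. The number of such dates is not given and may be zero. One misplaced participant adds up to 2.5 points at 40 controls.

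The baseline is a matter for clarification: about 0.2 mL on the planning value if the control clause is applied to VOTP, and zero if the protocol rule is programmed.

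The consequences stay within the period AE tables and the descriptive VOTP output. A reader might infer that the efficacy result is exposed. It is not: the Week 24 primary and secondary analyses, power and sample size do not use these rules.

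**What to change.** **SAP 6.4.2.1.** Add a rule for controls who received optional treatment. Where the AE end date, the first-report visit or date, or a judgement that the event is treatment-related can place onset relative to the optional initial treatment, that information decides the period. Events placed on or after that treatment are imputed to the later of the treatment date and the first day of the known month or year. Events placed before it keep the randomization anchor. Where no such information exists, state the chosen anchor openly and show the tables under both.

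**SAP 5.6.3.** Add the matching onset rule: for VOTP in TP, a TEAE is an AE that began or worsened on or after the optional initial treatment.

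**SAP 5.1.** Add that, for VOTP in TP, the effectiveness baseline is the last non-missing value before the optional initial treatment, normally the Week 24 image. Otherwise declare the departure from the protocol in Appendix 2.

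**Cost.** Three short additions and minor programming. Even with full first-report information, about 5–6% of undated true CP events (those starting in the gap of at most 10 days between Week 24 and injection) may move to VOTP, the conservative direction for device safety. The documents do not show that the database holds a first-report field, so the sponsor should confirm this before finalizing the wording. The gain is smallest for month-only dates, where more than about 34% of the events must truly be post-injection for the change to reduce total misplacement.

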6.4.2.2. Missing/Incomplete AE End Date

For scenario 2, i.e. if day is missing but month and year are available, then the imputed day will be the last day of the month or the study exit date if they have the same month and year, whichever is earlier.

For scenario 4, i.e. if day and month are missing but year is available, then the imputed day and month will be 31 Dec., or the study exit date if they have the same year, whichever is earlier

For scenario 8, i.e. if day, month and year are all missing, then the imputed date will be the latest possible date on or before study exit date.

7. References

ALLERGAN

SAP 1894-701-008 Voluma Nose China
